5.3 ENROLLMENT AND RANDOMIZATION

There will be 18 participants per group (15 vaccine recipients and 3 placebo recipients). Investigators will be blinded to vaccine versus placebo within each group but not across groups. Participants will be block randomized. Group 1 (with a prime of Env-C Plasmid DNA IM alone at weeks 0, 4, 12) will be fully enrolled first. After the 18 participants in Group 1 are enrolled, the remaining groups, 2-7, will begin enrolling participants. Once 24 participants in Groups 2-7 have been enrolled (four from each group) and received their first vaccinations, enrollment and vaccinations in Groups 2-7 will be paused for the time it takes the PSRT to review (typically 3 to 14 days) blinded safety data from these 24 participants covering the period immediately after their first vaccination through Day 7. If it is determined to be necessary by the PSRT, the MHRP SMC will be consulted to review unblinded data to provide a recommendation on continuing enrollment.

When safety has been confirmed with PSRT review, the remaining 14 participants in each of Groups 2-7 will be enrolled, and vaccinations will continue until the first 24 participants in Groups 2-7 (four per group) have received their first boost dose (at 20 weeks—to create a time gap between boost vaccinations of the first cohort and the remaining study participants).

A second scheduled pause (this pauses boost vaccinations only; prime vaccinations can continue) will occur for Groups 2-7 after the same set of participants reviewed during the first scheduled pause (the first 24 participants (four per group) from Groups 2-7) has received its first boost (Group 1 can continue receiving vaccinations). This pause will review blinded safety data from these 24 participants, covering the period from the first boost through Day 7 after that boost. At both scheduled pauses, the PSRT will consult the SMC regarding the pause if either of the following conditions are met: 1) one (or more) participants experience an SAE that is related to a study agent, or 2) two (or more) participants experience grade 3 or 4 AEs of the same type (e.g. elevated ALT) related to a study agent. Boost vaccinations for Groups 2-7 will resume once safety data from the booster sentinel cohort have been reviewed by the PSRT and they have concluded it is safe to proceed.

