7.2 ANALYSIS

7.2.1 POWER AND SAMPLE SIZE

The safety, reactogenicity, and tolerability of the vaccine regimens are the primary endpoints for this study. Below in Table 6, the estimated probability of a participant having at least one of these events (in percent), along with the associated exact Clopper-Pearson 95% confidence interval, is given for various numbers of observed events that correspond to approximate event rates within study groups of possible interest. Note that some event rates cannot be exactly observed within a given group, depending on the sample size (e.g. 10% of 15 participants is 1.5 participants, which is rounded to 2 in the table below).

Table 5: Estimated probability (in percent) of a participant having at least one AE, along with the associated exact Clopper-Pearson 95% CI, given varying sample sizes and numbers of participants with at least one observed AE

Group	n	Approximate AE Rate ¹							
		0%		10%		20%		50%	
		Corresponding # AEs ²	Estimated Probability (95% CI)	Corresponding # AEs ²	Estimated Probability (95% CI)	Corresponding # AEs ²	Estimated Probability (95% CI)	Corresponding # AEs ²	Estimated Probability (95% CI)
Each Individual Group	15	0	0 (0, 21.8)	2	13.3 (1.7, 40.5)	3	20 (4.3, 48.1)	8	53.3 (26.6, 78.7)
Placebo	21	0	0 (0, 16.1)	2	9.5 (1.2, 30.4)	4	19 (5.4, 41.9)	11	52.4 (29.8, 74.3)
Any DNA Prime with HIV Env gp145 C.6980 /Rehydragel Boosts	105	0	0 (0, 3.5)	11	10.5 (5.3, 18.0)	21	20 (12.8, 28.9)	53	50.5 (40.5, 60.4)
DNA alone (1+2), DNA+TCI (3+4), DNA/ALF43 (5+6)	30	0	0 (0, 11.6)	3	10 (2.1, 26.5)	6	20 (7.7, 38.6)	15	50 (31.3, 68.7)
HIV Env gp145 C.6980 /Rehydragel boost (1+3+5), HIV Env gp145 C.6980 /Rehydragel/ALF43 boost (2+4+6)	45	0	0 (0, 7.9)	5	11.1 (3.7, 24.1)	9	20 (9.6, 34.6)	23	51.1 (35.8, 66.3)
Any ALF43	75	0	0 (0, 4.8)	8	10.7 (4.7, 20.0)	15	20 (11.6, 30.8)	38	50.7 (38.9, 62.4)

¹ The approximate proportion of participants in a group reporting at least one event of interest

² The number of participants with observed event(s) needed to most closely correspond to the given approximate event rate, with the given sample size

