For illustration, if 2 individuals among the 15 participants in an individual vaccine group experienced at least one event, the estimated event probability would be 13.3%, with an associated exact 95% CI of (1.7%, 40.5%). Eleven individuals reporting at least one event among all active participants (n=105) would lead to a similar estimated event probability of 10.5%, but with a narrower exact 95% CI (5.3%, 18%).

The table below gives the probability of observing at least one or more than one event in a group of interest, given underlying per-subject probabilities of at least one event.

Table 6: Probability of observing at least one or at least two safety events in a given group, given varying underlying per-participant probabilities of experiencing at least one event

Group	n	Underlying Probability of At Least One Event					
		1%		10%		20%	
		>0	>1	>0	>1	>0	>1
Each Individual Vaccine Group	15	14.0%	1.0%	79.4%	45.1%	96.5%	83.3%
Placebo	21	19.0%	1.9%	89.1%	63.5%	>99%	94.2%
Any Env-C Plasmid DNA Prime with HIV Env gp145 C.6980 /Rehydragel Boosts	105	65.2%	28.3%	>99%	>99%	>99%	>99%
Env-C Plasmid DNA alone (1+2), Env-C Plasmid DNA+TCI (3+4), Env-C Plasmid DNA/ALF43 (5+6)	30	26.0%	3.6%	95.8%	81.6%	>99%	>99%
HIV Env gp145 C.6980 /Rehydragel boost (1+3+5), HIV Env gp145 C.6980 /Rehydragel/ALF43 boost (2+4+6)	45	36.4%	7.5%	>99%	94.8%	>99%	>99%
Any ALF43	75	52.9%	17.3%	>99%	>99%	>99%	>99%

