7.2.2 PRIMARY ANALYSIS

The primary endpoints of this Phase 1 study are related to the safety, reactogenicity and tolerability of the Env-C Plasmid DNA vaccine regimens. These will be monitored by PSRT and SMC as appropriate, and SAE), AEs and PIMMC will be recorded until the end of the trial.

SAEs, AEs, AESIs, reactogenicity, and tolerability will be tabulated by study group and combinations of interest. Exact 95% Clopper-Pearson confidence intervals will be calculated for each set of events, and the maximum severity and relatedness will be reported for each participant. While the study was not designed with the purpose of detecting safety differences, comparisons between regimens or between groups of interest and the placebo controls may be made. These comparisons would be made at a two-sided $\alpha=0.05$ level, using the normal approximation to the binomial distribution (z-test) as mentioned in the previous section, or an alternate testing procedure as appropriate (e.g. Fisher's Exact test for smaller samples). No adjustments for multiple comparisons will be made.

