7.2.3 SECONDARY ANALYSIS

The secondary endpoints of this study involve the immune response to the vaccination regimens in either the systemic and mucosal compartments. The laboratory assays used to measure these various immune response endpoints typically result in continuous measurements for each participant.

For each continuous immune response variable of interest, means, medians, ranges and 95% Wald confidence intervals will be computed. Proportions and exact 95% Clopper-Pearson confidence intervals will be computed for any categorical variables.

Comparisons of these endpoints between study groups may be made using non-parametric Mann-Whitney U tests, and once again, no adjustments for multiple comparisons will be made due to the hypothesis- generating nature of the study. The groups will be the same as used for the safety comparison but also may include other groups. For any categorical secondary endpoints, Fisher's Exact tests or asymptotic tests assuming normality will be used as appropriate.

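### For categorical secondary endpoints, 7.2.3 permits two tests that sit on either side of 5% and can disagree; naming Boschloo's exact test would hold the level and, at 15 v 15, gain about 14-16 points of power over Fisher

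*Protocol*

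**What the plan says.** Protocol 7.2.3 summarises categorical secondary variables as proportions with exact Clopper-Pearson intervals. For tests between groups it says: "For any categorical secondary endpoints", Fisher's "Exact tests or asymptotic tests assuming normality will be used as appropriate". It gives no rule for choosing between the two and no significance level.

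The nearest guidance is in 7.2.2, on the safety comparisons. These are made at the "two-sided $\alpha=0.05$ level" with a z-test, or with an alternative such as Fisher's "Exact test for smaller samples".

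On which groups are compared, 7.2.3 says: "The groups will be the same as used for the safety comparison but also may include other groups". Section 5.3 fixes the single-group size: "There will be 18 participants per group (15 vaccine recipients and 3 placebo recipients"). Table 5 in 7.2.1 adds pooled prime sets of 30, "DNA alone (1+2), DNA+TCI (3+4), DNA/ALF43 (5+6"), pooled boost sets of 45, and 21 placebo recipients.

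Section 7.2.3 also says that most assays give continuous values, compared by Mann-Whitney tests, that comparisons are optional and unadjusted, and that the purpose is to generate hypotheses. Section 7.2.4 foresees a later SAP that may change details.

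**The concern.** Fisher's test conditions on both margins. With 15 per group few tables are possible for given margins, so the attained type I error falls well below the nominal level, and the unused error is lost power. A reader applying the small-sample cue of 7.2.2 would choose Fisher for a comparison of two single regimens.

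The other permitted option, the normal approximation, has the opposite fault at these sizes: its type I error can exceed 5%. The choice is left open, so the same data can be significant or not depending on which test is later judged suitable. In an unadjusted screen of adjuvants with 15 vaccinees per regimen, both the lost power and the open choice work against the aim. One exact test avoids both.

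**Working it through.** **The plan's own figure.** The protocol gives no size or power for any between-group test, so there is none to reproduce.

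**Inputs.** Group sizes 15, 30, 45 and 21: 5.3 and Table 5. Two-sided 0.05: 7.2.2, assumed to carry over to 7.2.3. Response rates: assumptions, since the document gives none.

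**Method.** Let x and y be responders among n1 and n2, and R the set of tables a test rejects.
- Power(π1, π2) = sum over (x, y) in R of Bin(x; n1, π1) × Bin(y; n2, π2).
- Size = the maximum of the same sum over a common rate π1 = π2 = π, on a grid from 0.001 to 0.999.
- Fisher: R = tables with two-sided Fisher p ≤ 0.05.
- Boschloo: order tables by two-sided Fisher p and take the largest R whose size stays ≤ 0.05. With this ordering it rejects every table that Fisher rejects.
- z-test: R = tables with |z| > 1.96, where z = (x/n1 − y/n2) / √[p̄(1 − p̄)(1/n1 + 1/n2)] and p̄ = (x + y)/(n1 + n2).

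**Maximum size**

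| Groups | Fisher | Boschloo | z-test |
|---|---|---|---|
| 15 v 15 | 1.8% | 4.3% | 5.5% |
| 30 v 30 | 2.7% | 4.7% | 5.5% |
| 45 v 45 | 3.2% | 4.9% | 6.0% |
| 15 v 21 | 4.2% | 4.7% | 5.8% |

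At 15 v 15 the Boschloo region corresponds to a Fisher p-value cut-off of about 0.0996.

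**Power**

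| Groups | Assumed rates | Fisher | Boschloo | Gain (points) | z-test |
|---|---|---|---|---|---|
| 15 v 15 | 40% v 80% | 44.7% | 59.9% | 15.2 | 62.7% |
| 15 v 15 | 30% v 70% | 43.4% | 59.0% | 15.6 | 59.6% |
| 15 v 15 | 50% v 90% | 53.6% | 67.3% | 13.7 | 72.6% |
| 30 v 30 | 40% v 70% | 56.1% | 64.7% | 8.6 | 66.3% |
| 30 v 30 | 40% v 80% | 85.1% | 89.9% | 4.9 | 90.5% |
| 30 v 30 | 50% v 90% | 91.4% | 93.0% | 1.7 | 94.9% |
| 45 v 45 | 70% v 90% | 57.5% | 66.2% | 8.8 | 69.4% |
| 45 v 45 | 40% v 80% | 96.8% | 97.9% | 1.0 | 98.0% |

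Gains are taken from unrounded powers. At the larger sizes the gain is small where Fisher's power is already above 90%.

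Against placebo (15 v 21) the gain depends on which group responds more. With 40% in the group of 15 and 80% in the group of 21 it is 6.2 points (63.8% to 70.0%). With 40% in the 21 placebo recipients and 80% in the 15 vaccinees it is 0.3 points (67.0% to 67.3%).

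**One table, the two permitted tests: 12/15 v 6/15**
- Fisher, one tail: [C(15,12)C(15,6) + C(15,13)C(15,5) + C(15,14)C(15,4) + C(15,15)C(15,3)] / C(30,18) = (2,277,275 + 315,315 + 20,475 + 455) / 86,493,225 = 0.0302. The groups are equal, so two-sided p = 2 × 0.0302 = 0.060.
- z-test: p̄ = 18/30 = 0.6; z = 0.4 / √(0.6 × 0.4 × 2/15) = 0.4 / 0.1789 = 2.24; p ≈ 0.025.
- Boschloo: p = 0.030 with the two-sided Fisher ordering, or 0.032 by the SciPy routine, which doubles the one-sided value.

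For 13/15 v 7/15, Fisher gives 0.0502, the z-test about 0.020, and Boschloo 0.023 or 0.027.

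**The case against.** A reader might infer that the protocol commits response rates to Fisher's test, and that real adjuvant effects under the secondary objectives would therefore be missed. The documents do not support that. Section 7.2.3 allows an asymptotic test in the same sentence. The small-sample cue and the 0.05 level both come from the safety text, where Fisher is only an example. Under the permitted z-test the power loss disappears, and both worked tables are significant.

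The effect on the objectives is also limited. The first two secondary endpoints are antibody magnitude, durability and area under the curve. No responder definition is stated, and proportions with exact intervals are reported whichever test is used. Fisher controls type I error, so using it would be valid. The 14-16 points belong to balanced 15 v 15 comparisons with large assumed differences. The pooled sets of 30 and 45 are natural contrasts for the prime and boost questions, and there the gain is smaller. Finally, the choice of a two-sample test is often left to the SAP, and 7.2.4 anticipates one.

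All of this stands, and it limits the point to a conditional one. It does not remove it. The z-test recovers power partly by exceeding 5%, the two named options can reach different conclusions on the same data, and the text gives no rule for choosing between them for these endpoints.

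**Conclusion.** The point holds as a conditional efficiency and consistency improvement. If Fisher is chosen at 15 v 15, its size is at most 1.8%, and about 14-16 points of power are lost against Boschloo for assumed 40-point differences. The loss is about 2-9 points at 30 v 30 and 1-9 points at 45 v 45 for the rates tabulated, and between almost nothing and about 6 points at 15 v 21 for 40% v 80%. If the z-test is chosen, power is similar to or higher than Boschloo's, but the size can reach 5.5-6.0% at the balanced group sizes.

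This rests on a two-sided 0.05 level carried over from 7.2.2 and on assumed response rates. It bears only on categorical summaries in unadjusted, hypothesis-generating analyses. It is not an error of validity, and it does not touch the continuous endpoints that make up most of the secondary analysis.

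**What to change.** In 7.2.3, or in the SAP foreseen in 7.2.4, replace the choice between Fisher's and asymptotic tests with one sentence: two-group comparisons of categorical secondary endpoints use Boschloo's exact unconditional test at two-sided 0.05, with the two-sided Fisher p-value as the ordering statistic. Naming the ordering matters, because software that doubles a one-sided value gives slightly different p-values. Keep the Clopper-Pearson intervals as planned.

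The cost is one sentence and a standard software routine, with no added participants, samples or visits. The downside is a less familiar test name.

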7.2.4 EXPLORATORY AND SUBGROUP ANALYSES

Exploratory and subgroup analyses involve additional immune response endpoints as well as DNA microarrays. These will be analyzed similarly to the secondary endpoints. For any genetic analyses, control of the false discovery rate (FDR) at the 0.1 level will be made via p-value adjustment.

After the assays for the secondary and exploratory endpoints are finalized and before the final analyses have begun, a statistical analysis plan (SAP) will be created to elucidate upon these details and make any changes as necessary.

8 SAFETY AND REPORTING

8.1 ASSESSING AND RECORDING SAFETY PARAMETERS

8.1.1 REACTOGENICITY

8.1.1.1 Diary Card (7-Day Solicited Reactogenicity)

Reactogenicity events are AEs that are common and known to occur following administration of this type of study vaccine. A diary card will be used to aid in the collection of potential reactions.

Temperature and solicited local and systemic symptoms will be recorded in the clinic before vaccination and 30-60 minutes post-injection, at home about 6 hours after vaccination, and then daily by the participant for 7 days. Solicited symptoms that persist after the end of day 7 will be considered an AE or SAE, will be documented, and followed through resolution.

At each vaccination visit, participants will be given a new diary card, a thermometer and a ruler. The diary card will be used as a memory aid, on which the participant will record oral temperature, local and systemic symptoms, and concomitant medications daily for 7 days, beginning with the day of vaccination. Participants will be trained to complete the diary card, how to use the thermometer, and how to measure injection site swelling and redness using the ruler after each vaccination. Completion of the diary card training will be noted in source documents. The diary card is not a source document; the information gained from the review of the diary card and the interview with participants will be documented using a combination of progress notes and CRFs maintained in the participants research chart.

The solicited signs and symptoms on the diary card are:

Local

- Pain/tenderness
- Itching
- Warmth
- Redness/erythema measurement of largest dimension
- Swelling/induration measurement of largest dimension

Systemic

- Fever
- Myalgia
- Arthralgia
- Headache
- Fatigue
- Chills
- Rash
- Nausea

- Dizziness

Where multiple assessments are taken on the same day, participants will be requested to record the day's highest measured temperature and measurement of largest dimension for redness and swelling.

Follow-up on participant well-being will be performed by telephone (preferred method) or clinic visit on the day following vaccination (and up to 48 hrs. later). Diary cards will be reviewed with the clinician on day 7 ± 2 following each vaccination. If upon reviewing the diary card, the clinician finds that local or systemic information (except swelling, redness, temperature measurements) is missing from the diary card, or the diary card is lost, the participant will be asked to provide the missing information to the best of their recollection. The missing data, such as temperature measurements will be indicated as missing in the database and a lost diary card will not result in a protocol deviation.

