2.2.3 OVERVIEW OF RELEVANT CLINICAL STUDIES

Of the five components proposed in the RV460 vaccine regimen, both the Env-C Plasmid DNA (IND 17813; HVTN124) and the HIV Env gp145 C.6980 protein (IND 17766; HVTN122) vaccines are in clinical Phase 1 trials. Clinical data on the RV460-specific formulations of Rehydragel® or dmLT are published. The most significant data sets on HIV Env proteins (gp120) with Rehydragel® (AIDS VAX® vaccine), [46], [43], [63], [64], come from efficacy trials where the product was tested alone or in a prime-boost combination with a canarypox DNA vector (RV144) and compared to placebo. dmLT has been tested as both an antigen and adjuvant in an oral vaccine for enterotoxigenic *E. coli* (ETEC) diarrhea [65], [66], [58].

2.2.3.1 Safety and Immunogenicity of the Env-C Plasmid DNA Alone or with an HIV Env Protein Boost Vaccine

DNA plasmid vaccines expressing HIV-1 Env antigens have been tested in multiple clinical studies up to 8.0 mg/dose and have demonstrated an acceptable safety profile when administered alone or with adjuvanted HIV-1 Env proteins [28], [29], [30], [31], [32], [33], [34], [35] and other diseases [36]; for reviews see [37], [38], [39] HIV-1 DNA plasmid vaccines expressing HIV-1 Env antigens are safe and relatively well tolerated in humans. For some HIV-1 DNA Env preparations, pruritus or localized delayed-type hypersensitivity (DTH) reactions have occurred as non-serious, low-grade adverse events (AEs) attributed to the HIV-1 DNA vaccine; but they were not frequent or severe enough to halt their respective studies.

Although the single plasmid of Env-C Plasmid DNA vaccine has not been previously tested in humans, a first generation of the Env-C Plasmid DNA vaccine was tested as a multigene, polyvalent DNA prime-protein boost HIV-1 vaccine, DP6-001, with the same DNA plasmid backbone [26].

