In this study, each participant received two vaccine components; three sequential inoculations using a DNA plasmid vaccine administered either intradermally or intramuscularly followed by two sequential inoculations using a protein vaccine. This study involved 2 dose levels of DNA vaccines (1.2 mg [Groups A and B]; 7.2 mg [Group C]) expressing five gp120 Env antigens (HIV-1 clades A, B, C and E) and one Gag antigen (HIV-1 clade C), and a single dose level of the same five recombinant expressed gp120 protein vaccines, produced and purified from CHO cells, and mixed with QS21 adjuvant at the time of injection. Additionally, Group C in the previous trial received more than 3 times the dose of DNA compared to the 2 mg of Env-C Plasmid DNA proposed in RV460.

After each DNA immunization, Grade 1 or 2 fever was common, occurring in up to 42% of DNA vaccine recipients of which Group A (ID) recipients had significantly more frequent injection-site erythema after DNA vaccination than Groups B or C (IM). Local injection site reactions were most common (65% of participants) and included Type IV delayed-type hypersensitivity (DTH) reactions at prior DNA inoculation sites in 12 of 28 (43%) participants after protein vaccination [26]. The erythematous “recall” reactions at prior DNA vaccination sites typically appeared 36 to 72 hours after injection of the DNA (8 milder reactions) and the protein boost (12 mild to severe reactions).

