3.3 DOSAGE PREPARATION, DISPENSING AND ADMINISTRATION OF STUDY PRODUCT

The vaccines will be given by intramuscular (IM) injection into the deltoid muscle, excluding the dmLT adjuvant which is given by TCI. All products will be combined into one syringe (excluding dmLT) for IM injection, i.e., Env-C Plasmid DNA and HIV Env gp145 C.6980/ALF43A for study Group 7. Once combined, the vaccine regimen must be administered as soon as possible, although based on the stability data performed in our laboratory (data not shown but a comprehensive report was provided to DAIDS), all the vaccine formulations were stable for 24 hours. This is significantly more than required time to vaccinate a participant in the clinic. Alternating deltoids will be used for subsequent immunizations [63]. Vaccination in contralateral limbs has been successfully utilized to achieve prime boost in multiple vaccine trials [63]. Alternating sites allowed for better attribution of local reactogenicity reactions.

The site for injection cleaned with an alcohol wipe before the injection. Since the interventions are vaccines, the concept of a washout period does not apply. The duration of the interventions is unknown, but it is hoped that it would be ten years or longer.

See IB and Package Inserts for further information on each study product.

126 healthy men and women between the ages of 18 and 40 years will be randomized to one of seven groups:

Table 3: Study Groups

Group	N V/P	Prime at weeks 0, 4, 12	Boost at weeks 20, 32, 56
1	15/3	Env-C Plasmid DNA (2 mg, IM)	HIV Env gp145 C.6980 (100 µg, IM)/Rehydragel® (500 µg, IM)
2	15/3	Env-C Plasmid DNA (2 mg, IM)	HIV Env gp145 C.6980 (100 µg, IM)/Rehydragel® (500 µg, IM) / ALF43 (200 µg, IM)
3	15/3	Env-C Plasmid DNA (2 mg, IM) + dmLT (50 µg, TCI)	HIV Env gp145 C.6980 (100 µg, IM)/Rehydragel® (500 µg, IM)
4	15/3	Env-C Plasmid DNA (2 mg, IM) + dmLT (50 µg, TCI)	HIV Env gp145 C.6980 (100 µg, IM)/Rehydragel® (500 µg, IM) / ALF43 (200 µg, IM)
5	15/3	Env-C Plasmid DNA (2 mg, IM) / ALF43 (200 µg, IM)	HIV Env gp145 C.6980 (100 µg, IM)/Rehydragel® (500 µg, IM)
6	15/3	Env-C Plasmid DNA (2 mg, IM) / ALF43 (200 µg, IM)	HIV Env gp145 C.6980 (100 µg, IM)/Rehydragel® (500 µg, IM) / ALF43 (200 µg, IM)
7	15/3	Env-C Plasmid DNA (2 mg, IM) /HIV Env gp145 C.6980 (100 µg, IM)/ALF43 (200 µg, IM)	Env-C Plasmid DNA (2 mg, IM) /HIV Env gp145 C.6980 (100 µg, IM)/ALF43 (200 µg, IM)/Rehydragel® 500 µg, IM)

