APPENDIX I. DIARY CARD

LABEL

Diary Card

Participant ID: | 4 | 6 | 0 | - | | | | | |

Vacc. #: _____

Vaccination Date: _____

DD

MM

YYYY

Short title: Comparative Adjuvant Study for HIV-1 Env DNA and Protein Vaccines in Kenya
 RV460 / WRAIR #2672

13-07-2020
 Version 1.7

Instruction for recording No. 2-7 and 8-15

Please use the grading scale below to record the severity of your reaction to the injections in the next sections:

0 = None**1 = Mild:** minimal interference with usual social and functional activities.**2 = Moderate:** symptoms causing greater than minimal interference with usual social and functional activities.**3 = Severe:** symptoms causing inability to perform usual social and functional activities

Time After vaccination	30-60 min	6 hr	Day 1	Day 2	Day 3	Day 4	Day 5	Day 6	Day 7
Day/Month	__ / __	__ / __	__ / __	__ / __	__ / __	__ / __	__ / __	__ / __	__ / __
Time taken (hrs/min)									
1. Oral temperature (Celsius)									

Vaccination injection site reactions		 Right arm		 Left arm	
2. Injection site pain or tenderness					
3. Swelling (at injection site)					
4. Itching (at injection site)					
5. Redness (measure the largest dimension in cm.)					
6. Hardness (measure the largest dimension in cm.)					
7. Warmth (at injection site)					

General Reactions (not injection site)								
8. Headache								
9. Chills								
10. Dizziness								
11. Tiredness / Fatigue								
12. Nausea								
13. Muscle pain								
14. Joint pain								
15. Rash (if present, describe in "other symptoms")								
16. Took medication for fever or for above symptoms?	0=No 1=Yes							

Other symptoms (please describe):								

LABEL

Diary Card

Participant ID: | 4 | 6 | 0 | - | | | | |

Vacc. #: _____

Vaccination Date: _____

DD

MM

YYYY

Short title: Comparative Adjuvant Study for HIV-1 Env DNA and Protein Vaccines in Kenya
 RV460 / WRAIR #2672

13-07-2020
 Version 1.7

If you take any medication, please record in the table below
 If you take medications for fevers, please check your temperature again after 4 hours and record above in "Other symptoms"

Medication	Dose/route	Reason	Start date	Stop date

Suggestion

- Complete the diary card in as much detail as you can every day, at the same time each day
- Record any problems that occur during this period
- Bring back this diary card with you at the next appointment
- If you forget to record any data, leave it blank

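### The solicited local items do not ask about earlier DNA injection sites, where the predecessor trial saw recall (DTH) reactions in 12 of 28 participants after protein boosting

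*Protocol*

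**What the plan says.** Protocol Section 2.2.3.1 presents DP6-001 as the direct predecessor: "a first generation of the Env-C Plasmid DNA vaccine was tested as a multigene, polyvalent DNA prime-protein boost HIV-1 vaccine, DP6-001", on the same plasmid backbone. It reports "delayed-type hypersensitivity (DTH) reactions at prior DNA inoculation sites in 12 of 28 (43%) participants after protein vaccination". On timing it says that "reactions at prior DNA vaccination sites typically appeared 36 to 72 hours after injection of the DNA (8 milder reactions"). The same sentence counts 12 reactions after protein boosting and grades them from mild to severe.

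Section 8.1.1.1 defines reactogenicity as adverse events that are both common and known for this type of vaccine. It lists five local items (pain, itching, warmth, redness, swelling) and trains participants in "how to measure injection site swelling and redness using the ruler after each vaccination". The diary card in Appendix I, one per vaccination, puts all local items in one block with a right/left arm box, worded as in "3. Swelling (at injection site"). Rash stands in the separate block for reactions away from the injection site, and Section 8.1.1.1 classes it as systemic.

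Deltoids alternate between doses, with the reason given in Section 3.3: "Alternating sites allowed for better attribution of local reactogenicity reactions". Section 1.2.1 makes solicited local and systemic reactogenicity, together with related AEs and SAEs, the primary endpoint.

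**The concern.** By the protocol's own account, recall reactions at old DNA sites were frequent in the closest earlier regimen, and their onset falls inside the seven-day diary. They therefore meet Section 8.1.1.1's own description of what should be solicited. The instrument does not ask for them.

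Two kinds of misfiling can follow. A recall reaction in the opposite arm has no local row, so it is likely to appear as systemic rash or as free text. One in the same deltoid can be entered as part of the reaction to the new injection. The first lowers the local rate and raises the systemic one; the second raises the current-site rate. The net direction cannot be predicted. What is at stake is the quality of the per-group local reactogenicity rates after boosting, which belong to the primary endpoint. The second scheduled pause also reviews exactly this window, from the first boost to Day 7 after it (Section 5.3). Similar reactions scattered under different terms are harder to recognise there as one pattern.

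**Working it through.** **1. The protocol's figure.** 12/28 = 0.4286, which rounds to the stated 43%. The exact (Clopper-Pearson) 95% limits are the 2.5% quantile of Beta(12, 17) and the 97.5% quantile of Beta(13, 16): 24.5% and 62.8%.

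**2. Where the old DNA sites lie at each boost.** Under strict alternation (Sections 3.3 and 3.3.4), doses 1, 3 and 5 go in arm A and doses 2, 4 and 6 in arm B. For Groups 1 to 6, where DNA is given at doses 1 to 3 only:

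| Boost dose (week) | Arm | Earlier DNA sites, same arm | Earlier DNA sites, opposite arm | Clinic visit at day 3 | Clinic visit at day 7 |
|---|---|---|---|---|---|
| 4 (20) | B | 1 (dose 2) | 2 (doses 1, 3) | yes, day 143 | yes, day 147 |
| 5 (32) | A | 2 (doses 1, 3) | 1 (dose 2) | none | yes, day 231 |
| 6 (56) | B | 1 (dose 2) | 2 (doses 1, 3) | yes, day 395 | yes, day 399 |

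So, by default, every boost finds at least one old DNA site in each arm. In Group 7 the boosts also contain DNA, which adds sites. Section 3.3.4 lets the investigator use the same arm again, so the pattern is the default and not a certainty.

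**3. What could still catch a recall reaction.**
- The rash item (graded 0 to 3) and the free-text field: no size is asked for, and rash counts as systemic.
- The contact at 24 to 48 hours (Section 8.1.1.1; Appendix A, note 6): it can come before an onset at 36 to 72 hours.
- The targeted examination and diary review at day 7 after every dose, and at day 3 after doses 1, 3, 4 and 6. Section 8.1.1.1 exempts missing redness and swelling measurements from being filled in by recollection, so a size not noted at home is not recovered at the review.
- General AE documentation (Section 8.1.3).

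**4. Illustrative size, if the earlier rate carried over (assumption).** There are 7 × 15 = 105 vaccine recipients; the 21 placebo recipients get saline and are not counted.
- Full rate: 105 × 0.4286 = 45 (105 × 0.245 to 105 × 0.628, about 26 to 66). Per group: 15 × 0.4286 = 6.4 (3.7 to 9.4).
- A quarter of the rate: 0.4286/4 = 0.107, and 105 × 0.107 = 11.

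**5. The pooled boost contrast.** Section 7.2.1 pools Groups 1+3+5 against 2+4+6. By Table 1 each side holds 15 vaccine recipients with DNA alone, 15 with DNA + dmLT and 15 with DNA/ALF43. If recall occurs at rates r1, r2 and r3 under the three primes, the expected count on each side is 15(r1 + r2 + r3), and the difference is zero.

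**The case against.** The strongest reply is that not soliciting a reaction is different from not capturing it. The diary is a memory aid. The record comes from diary review and interview, participants are examined at follow-up visits, all AEs are documented regardless of relationship, and an AE judged related is in the primary endpoint whether solicited or not. The earlier reactions were erythematous, so the rash item gives them a graded place. The list in Section 8.1.1.1 also does not itself restrict the local items to the newest site; that restriction is read from the card and the training sentence. All of this stands. A reader might infer that recall reactions would be lost from the primary endpoint, and the documents do not support that. What is lost is systematic, measured recording by site.

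A second reply concerns the 43%. It pools intradermal and intramuscular recipients, DNA doses of 1.2 and 7.2 mg, and protein given with QS21. RV460 gives 2 mg of one plasmid intramuscularly and one protein with other adjuvants. Section 2.2.3.1 also describes such reactions, for some other DNA preparations, as non-serious and low-grade. This stands too: the rate shows that the reaction is known, but it does not forecast its frequency here.

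A reader might also infer that misfiled recall reactions bias the comparison of Rehydragel with Rehydragel plus ALF43 when recall differs by prime. Step 5 shows that they do not, because the primes are balanced across the two pooled sides. If recall instead depends on the boost adjuvant, it is a genuine effect of the boost. Section 7.2.2 adds that the study was not designed to detect safety differences.

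**Conclusion.** The point holds as a weakness of the data-collection instrument. The protocol documents recall reactions at earlier DNA sites as frequent in the predecessor regimen, yet no solicited item asks about those sites. Such reactions would reach the database by general routes, without a size measurement, and in the same deltoid they may be merged with the new reaction. Site-specific ascertainment and per-group local rates after boosting are weaker for it. The pooled boost contrast is not biased through prime differences, and nothing in the protocol is miscalculated.

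The size is uncertain. Projections of about 45 of 105 at the full earlier rate and about 11 of 105 at a quarter of it rest on carrying over a rate from other routes, doses and adjuvants. The structural finding does not depend on either number. It rests on reading the card's injection-site block as referring to the vaccination named on that card, which is its natural meaning. The dose-by-dose picture also assumes the default alternation of arms.

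**What to change.** - From dose 2 onward, add one diary row and a matching CRF item, on every participant's card, for redness, swelling or itching at an earlier injection site. Record the arm, the largest dimension in cm, and the dose number where it can be identified. Section 3.3.4 already has the arm used for vaccination captured on the CRF, so the dose can often be traced.
- Inspect both deltoids at visits that already exist: day 7 after every dose, and day 3 after doses 3, 4 and 6 (the day-3 visit after dose 1 precedes any earlier site). Doses 2 and 5 have no day-3 visit, so at 36 to 72 hours the diary row carries the weight there.
- Tabulate recall reactions separately from current-site reactions, by group and dose, with the exact intervals already planned in Section 7.2.2.

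The cost is a slightly longer diary, one CRF item and a little training. No new visit or procedure is needed.
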